10.5.1.2 Sensitivity Analyses of Co-Primary Endpoints

To evaluate the robustness of the primary analysis results, sensitivity analyses will be performed as follows:

- The primary analysis will be repeated on the CAS.
- Non-parametric analyses (Quade test) will be performed on the FAS and CAS.

10.5.1.3 Subgroup Analyses of Co-Primary Endpoints

Subgroup analyses on the co-primary efficacy endpoints will be conducted using the subgroups specified in [Section 7.4](#). Treatment effect differences among subgroups, which represent subgroup by treatment interactions, will be estimated and tested based on statistics from the subgroup repeated measures models.

For subgroup analyses, the data-derived stratification factor (ie, screening LDL-C level and baseline statin use) will be used.

10.5.1.4 Additional Analyses of Co-Primary Endpoints

The co-primary endpoints will also be assessed within each dose frequency using dose frequency matched control (ie, evolocumab Q2W SC plus placebo PO QD vs ezetimibe QD plus placebo Q2W SC; evolocumab QM SC plus placebo PO QD vs. ezetimibe QD plus placebo QM SC) and pooled ezetimibe (ie, evolocumab Q2W vs. pooled ezetimibe; evolocumab QM vs. pooled ezetimibe).

In addition, the difference between the evolocumab Q2W and evolocumab QM groups will be estimated.

10.5.2 Analyses of Secondary Efficacy Endpoints

The statistical model and testing of the tier 1 co-secondary efficacy endpoints will be similar to the primary analysis of the co-primary endpoints. The co-secondary efficacy

endpoints of LDL-C response will be analyzed using the Cochran-Mantel Haenszel (CMH) test adjusted by the stratification factor.

Analyses of the tier 2 co-secondary efficacy endpoints will use the same analysis model as the tier 1 endpoints, and the testing will use a union-intersection test.

Multiplicity adjustment procedures are defined in [Section 10.1](#).

10.5.3 Analyses of Tertiary Efficacy Endpoints

Analysis of the tertiary efficacy endpoints will be similar to the primary analysis of the co-primary endpoints. No multiplicity adjustment will be applied

10.5.4 Analyses of Exploratory Endpoints

Exploratory endpoints related to lipid parameters, and hsCRP will be summarized by treatment group and by scheduled visit using descriptive statistics.

Non-coronary revascularizations will be collected on the eCRF. Subject incidence of exploratory endpoint events will be summarized for each treatment group.

10.6 Safety Analyses

10.6.1 Adverse Events

The Medical Dictionary for Regulatory Activities (MedDRA) version 20.1 or later will be used to code all events categorized as adverse events (AEs) to a system organ class and a preferred term. Severity of AEs will be graded using the CTCAE ([Appendix C](#)) and recorded on the eCRF. All adverse event tables will be summarized by actual treatment group. Treatment-emergent adverse events are events with an onset after the administration of the first dose of IP.

The subject incidence of AEs will be summarized for all TEAEs, serious TEAEs, TEAEs leading to withdrawal of investigational product, treatment-related TEAE and fatal TEAEs.

Subject incidence of all TEAEs, serious TEAEs, TEAEs leading to withdrawal of investigational product, and fatal TEAEs will be tabulated by system organ class and preferred term in descending order of frequency.

All TEAEs, serious TEAEs and TEAEs leading to withdrawal of investigational product will also be summarized by subgroups of age (< 65 years, ≥ 65 years; < 75 years, ≥ 75 years) and baseline statin use (Yes, No).

Subject incidence of TEAEs related to a device will be tabulated by preferred term in descending order of frequency.

Subject incidence of adverse events associated with injectable protein therapies:

- Injection site reactions
- Hypersensitivity or allergic reactions

will be summarized by category and preferred term. Neurocognitive events will also be summarized.

10.6.2 Laboratory Test Results

Descriptive statistics will be provided for actual values and changes from baseline in select laboratory parameters at each protocol-specified scheduled visit. Laboratory analytes are provided in the protocol [section 7.2](#). Lab shift tables using the CTCAE v4.03 or later grading will be used for the select analytes of interest, when applicable.

In addition, CK and liver function test (LFT) abnormalities will be assessed by the incidence overall and by visits of the following categories:

- CK > 5 x ULN
- CK > 10 x ULN
- ALT or AST > 3 x ULN
- ALT or AST > 5 x ULN
- Total bilirubin > 2 x ULN
- (ALT or AST > 3 x ULN) and Total bilirubin >2 x ULN and Alkaline Phosphatase < 2 x ULN

10.6.3 Vital Signs

Systolic and diastolic blood pressure and heart rate will be summarized by treatment group using descriptive statistics at each scheduled visit.

10.6.4 Antibody Formation

The incidence and percentages of subjects who develop anti-evolocumab antibodies (binding and if positive, neutralizing) at anytime will be tabulated.

10.6.5 Exposure to Investigational Product

Descriptive statistics will be produced to describe the patient-month exposure to SC IP, the categorical representation of dose received, and the total quantity of oral IP used (for the double-blind treatment period only) by randomized treatment group. Exposure definitions are provided in [Section 6.3](#).

10.6.6 Exposure to Concomitant Medication

For each part of the study, the number and proportion of subjects receiving selected lipid regulating medications captured on the Concomitant Medications eCRF will be

summarized by category and preferred term for each treatment group as coded by the World Health Organization Drug (WHODRUG) dictionary. Summaries will be provided for baseline use and use during each part of the study. The subject incidence of changes in lipid regulating medications during the double-blind treatment period and open-label extension period will also be provided.

11. Changes From Protocol-specified Analyses

Analysis of physical measurements will not be performed, because post-baseline measurements only occur at week 52.

12. Literature Citations / References

Hochberg Y. A sharper Bonferroni procedure for multiple tests of significance. *Biometrika* 1988;75:800-802.

Wiens BL. A fixed sequence Bonferroni procedure for testing multiple endpoints. *Pharmaceut. Statist.* 2003; 2:211-215

Japan Atherosclerosis Society (JAS) Guidelines for Prevention of Atherosclerotic Cardiovascular Diseases 2017

13. Appendices

Appendix A. Framingham Risk Score (FRS)

Method to calculate the Framingham Risk Score (FRS):

The β coefficients given in the two tables below are used to compute a linear function. The latter is corrected for the averages of the participants' risk factors (mean) from the Framingham study, and the subsequent result is exponentiated and used to calculate a 10-year probability of HCHD after insertion into a survival function ([Wilson et al](#)).

The calculation is different for men and women and use the following coefficients β_i , where i represents each of the independent variables. The values below are from the Framingham heart study (<http://www.framinghamheartstudy.org/risk-functions/coronary-heart-disease/hard-10-year-risk.php>).

t_chol = total cholesterol, hdl = HDL-C, sbp = systolic blood pressure, trt_htn = treatment for hypertension (if $sbp > 120$), $smoker$ = current smoker

Men			Women		
Independent variable	Coefficient β_i	mean	Independent variable	Coefficient β_i	mean
ln(age)	52.00961	3.8926095	ln(age)	31.764001	3.9213204
ln(t_chol)	20.014077	5.3441475	ln(t_chol)	22.465206	5.3628984
ln(hdl)	-0.905964	3.7731132	ln(hdl)	-1.187731	4.0146369
ln(sbp)	1.305784	4.8618212	ln(sbp)	2.552905	4.8376494
trt_htn (sbp>120)	0.241549	0.1180474	trt_htn (sbp>120)	0.420251	0.142802
smoker	12.096316	0.335602	smoker	13.07543	0.3236202
ln(age)* ln(t_chol)	-4.605038	20.8111562	ln(age)* ln(t_chol)	-5.060998	21.0557746
ln(age)*smoker ¹	-2.84367	1.2890301	ln(age)*smoker ²	-2.996945	1.2519882
ln(age)*ln(age)	-2.93323	15.2144965			
¹ if age>70 then ln(70)*smoker			² if age>78 then ln(78)*smoker		

The steps to determine the FRS is the same for men and women.

Men

For each subject:

1. Calculate $L_{men} = \beta_{ln(age)} * ln(age) + \beta_{ln(t_chol)} * ln(t_chol) + \beta_{ln(hdl)} * ln(hdl) + \beta_{ln(sbp)} * ln(sbp) + \beta_{trt_htn} * (if trt_htn) + \beta_{smoker} * (if smoker) + \beta_{ln(age)*ln(t_chol)} * ln(age)*ln(t_chol) + \beta_{ln(age)*smoker} * ln(age)*(if smoker) + \beta_{ln(age)*ln(age)} * ln(age)*ln(age)$
2. Calculate $A_{men} = L_{men} - 172.300168$ (note: the value of 172.300168 was derived based on the mean columns in above table)
3. Calculate $B_{men} = \exp (A_{men})$

4. Calculate $P_{men} = 1 - 0.9402^B_{men}$
5. $FRS_{men} = P_{men} * 100$ (rounded to nearest integer)

Women

For each subject:

1. Calculate $L_{women} = \beta_{ln(age)} * ln(age) + \beta_{ln(t_chol)} * ln(t_chol) + \beta_{ln(hdl)} * ln(hdl) + \beta_{ln(sbp)} * ln(sbp) + \beta_{trt_htn} * (if\ trt_htn) + \beta_{smoker} * (if\ smoker) + \beta_{ln(age)*ln(t_chol)} * ln(age) * ln(t_chol) + \beta_{ln(age)*smoker} * ln(age) * (if\ smoker)$
2. Calculate $A_{women} = L_{women} - 146.5933061$ (note: the value of 146.5933061 was derived based on the mean columns in above table)
3. Calculate $B_{women} = \exp(A_{women})$
4. Calculate $P_{women} = 1 - 0.98767^B_{women}$
5. $FRS_{women} = P_{women} * 100$ (rounded to nearest integer)

Notes

- For men, if subject is > age 70, then use $ln(70) * smoker$
- For women, if subject is > age 78, then use $ln(78) * smoker$
- For dichotomous variables trt_htn and $smoker$ use 1/0 to represent yes/no respectively
 - If a subject has $sbp \leq 120$ mmHg, then trt_htn is no

Calculated scores should match the interactive calculator

<http://cvdrisk.nhlbi.nih.gov/calculator.asp>

Appendix B. Analytical Study Week Assignments

Selected endpoints will be summarized by scheduled study visits in descriptive analyses.

Since the actual visits may not exactly coincide with their scheduled visit day, the actual visit day is mapped to the study visit generally by non-overlapping consecutive intervals covering the entire time continuum. The mapping intervals for all distinct schedules are summarized in the following tables.

Scheduled Visit Week	Week 2	Week 8	Week 10	Week 12	Week 24	Week 36	Week 48	Week 52	Week 54 EOS Phone Call
Scheduled Visit Day	15	57	71	85	169	253	337	365	379
Vital Signs		(1, 63]	(63, 77]	(77, min(91, first dose date of OLE)]	(min(91, first dose date of OLE), 210]	(210,294]	(294,350]	>350	
Fasting Lipids	(1, 35]	(35, 63]	(63, 77]	(77, min(91, first dose date of OLE)]	(min(91, first dose date of OLE), 210]	(210,294]	(294,350]	(350,378]	
Lp(a), ApoA1, ApoB			(1, 77]	(77, min(91, first dose date of OLE)]	(min(91, first dose date of OLE), 210]	(210,294]	(294,350]	(350,378]	
PK, PCSK9	(1, 42]		(42, 77]	(77, min(91, first dose date of OLE)]				(min(91, first dose date of OLE), 378]	
Hematology and Chemistry		(1, 70]		(70, min(91, first dose date of OLE)]				> min(91, first dose date of OLE)	
Physical Exam, hsCRP, Urinalysis, HbA1c, Biomarkers, anti-evolocumab antibodies				(1, min(91, first dose date of OLE)]				> min(91, first dose date of OLE)	
Weight, waist circumference								> 1	

Handling multiple records assigned to an analytical study week:

If there is more than one record in a study week interval, the analytical record for that specific study week will be defined as the record closest to the scheduled visit day of that specific study week ($7 \times$ study week + 1). If two records are equidistant from the scheduled day, then the earlier record will be chosen. If there are multiple records on the same day, the last record will be used.

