Abbreviation or Term	Definition/Explanation
OLEAS	Open Label Extension Analysis Set
PBO	Placebo
PCI	Percutaneous coronary intervention
PCSK9	Proprotein convertase subtilisin/kexin type 9
PKPD	Pharmacokinetic / pharmacodynamics
PO	Oral administration
Q2W	Q2W is defined as every 2 weeks with a window of \pm 3 days
Q4W	Every 4 weeks, (AMG 145 Background Section)
QD	Each day
QM	QM is defined as every 4 weeks with a window of \pm 7 days
QW	Every week
Randomized	Assignment to treatment group based on computer-generated randomization schedules prepared by Amgen before the start of the study
RAS	Rechallenge Analysis Set
RBC	Red blood cells
RR	Respiratory rate
SBP	Systolic blood pressure
SC	Subcutaneous
SD	Standard deviation
SF-36	Short Form (36) Health Survey
Source Data	Information from an original record or certified a copy of the original record containing patient information for use in clinical research. The information may include, but is not limited to, clinical findings, observations, or other activities in a clinical trial necessary for the reconstruction and evaluation of the trial. Source data are contained in source documents (original records or certified copies). (ICH Guideline (E6)). Examples of source data include Subject ID, Randomization ID, and Stratification Value.
TBL	Total bilirubin
TIA	Transient ischemic attack
Tmax	Time to maximum concentration
TSH	Thyroid stimulating hormone
ULN	Upper limit of normal
VLDL-C	Very low-density lipoprotein cholesterol
WBC	White blood cell

TABLE OF CONTENTS

Protocol Synopsis	3
Study 20140234 Treatment Schema	7
Study Glossary	8
1. OBJECTIVES	15
1.1 Primary	15
1.2 Secondary	15
2. BACKGROUND AND RATIONALE	15
2.1 Disease	15
2.2 Amgen Investigational Product Background	18
2.3 Non-Amgen Medicinal Product Background	19
2.4 Rationale	20
2.5 Clinical Hypotheses	21
3. EXPERIMENTAL PLAN	21
3.1 Study Design	21
3.2 Number of Sites	22
3.3 Number of Subjects	22
3.4 Replacement of Subjects	22
3.5 Estimated Study Duration	22
3.5.1 Study Duration for Subjects	22
3.5.2 End of Study	23
4. SUBJECT ELIGIBILITY	23
4.1 Inclusion and Exclusion Criteria	23
4.1.1 Inclusion Criteria	23
4.1.2 Exclusion Criteria	24
5. SUBJECT ENROLLMENT	27
5.1 Randomization/Treatment Assignment	27
5.2 Site Personnel Access to Individual Treatment Assignments	28
6. TREATMENT PROCEDURES	28
6.1 Classification of Product(s) and/or Medical Device(s)	29
6.2 Investigational Product	29
6.2.1 Amgen Investigational Product Evolocumab (AMG 145)	29

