The study includes collection of biomarker samples, where approved by the institutional review board (IEC/IRB). Administration of PO IP (ezetimibe or placebo) will end with the week 12 visit for all subjects. Following the week 12 visit, subjects should be treated to standard of care in addition to receiving open label evolocumab.

Subjects will be encouraged to complete all planned visits regardless of their adherence to investigational product (IP) administration. Formal review of the accumulating blinded data by an independent Data Monitoring Committee (DMC) **will occur**.

The study endpoints are defined in [Section 10.1.1](#).

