6.3 Other Study Related Definitions

Analytical Study Week Assignments

Analytical windows will be used to assign parameter measurements to study weeks.

The algorithm is provided in [Appendix B](#).

Actual Treatment Group

A subject's actual treatment group is the randomized treatment group, unless the subject receives treatment throughout the study that is different than the randomized treatment group assignment, in which case the actual treatment group is the treatment received.

Investigational Product (IP)

Blinded Period:

SC IP includes evolocumab SC 140 mg Q2W, evolocumab SC 420 mg QM and their corresponding SC placebo.

Oral IP includes ezetimibe PO 10 mg QD and placebo PO QD.

OLE: SC IP includes evolocumab SC 140 mg Q2W and evolocumab SC 420mg QM.

SC IP Exposure Period (Months) in Blinded Period

For each Q2W subject:

SC IP Exposure Period in Blinded Period = [min (EOS Date, the day before OLE day 1, Last SCBIPD + 14 days) - First SCBIPD + 1] / 365.25 * 12

For each QM subject:

SC IP Exposure Period in Blinded Period = [min (EOS Date, the day before OLE day 1, Last SCBIPD + 28 days) - First SCBIPD +1] / 365.25 * 12

Oral IP Exposure Period (Months) in Blinded Period

For each subject:

Oral IP Exposure Period = [min (EOS Date, the day before OLE day 1, Last POBIPD + 1 day) - First POBIPD + 1] / 365.25 * 12

SC IP Exposure Period (Months) in OLE

For each Q2W subject:

SC IP Exposure Period in OLE = [min (EOS date, last SCOLEIPD + 14 days) - First SCOLEIPD +1] / 365.25 * 12

For each QM subject:

SC IP Exposure Period in OLE = [min (EOS date, last SCOLEIPD + 28 days) - First SCOLEIPD +1] / 365.25 * 12

Study Exposure Period in Months

For each randomized subject:

Study Exposure Period = (EOS date – Randomization Date + 1) / 365.25 * 12

Treatment Emergent Adverse Event (TEAE)

Events categorized as Adverse Events (AEs) starting on or after first dose of investigational product as determined by the flag indicating if the adverse event started prior to the first dose of IP on the Events eCRF and up to 30 days after the last dose of IP date or EOS, whichever occurs first. Please see below for the definition of TEAE in blinded period and OLE.

TEAE	Summary period
Blinded period	Blinded period day 1 (the same as study day 1) through min(last dose date + 30 days, EOS date, the day before OLE day 1)
OLE	OLE day 1 through min(last dose date + 30 days, EOS date)

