Note that the definition of TEAE has been documented in FORM 000505 prior to the unblinding for the primary analysis.

Reflexive Approach for LDL-C and VLDL-C

For all analyses related to LDL-C and VLDL-C, unless specified otherwise, a reflexive approach will be used. When calculated LDL-C is less than 40 mg/dL or triglycerides are > 400 mg/dL, the UC LDL-C value from the same blood sample will be used instead of calculated LDL-C and the UC VLDL-C value from the same blood sample will be used instead of calculated VLDL-C, if available.

Achievement of LDL-C < 70 mg/dL

A subject has achievement of LDL-C < 70 mg/dL if the post-baseline LDL-C value at week 12 is less than 70 mg/dL. If the value is missing, the subject is considered without the achievement.

Mean achievement of LDL-C < 70 mg/dL at weeks 10 and 12 is defined using the mean of non-missing LDL-C values at those two timepoints (if one is missing, mean equals the available one).

7. Analysis Subsets

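### SAP Appendix B opens the Week 24 and Week 52 windows at Day 91 even when no open-label dose has been given, so a late pre-extension sample is labelled open-label and the subject has no Week 12 value.

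*SAP*

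**What the plan says.** SAP Section 6.3 assigns parameter measurements to study weeks by the windows in Appendix B. No other assignment rule is given for the efficacy model.

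- **Week 12, fasting lipids.** The interval is "77, min(91, first dose date of OLE", closed at the upper end. A sample on the day of the first OLE dose therefore still counts as Week 12 if that day is no later than Day 91.
- **Week 24, lipids, apolipoproteins, Lp(a) and vital signs.** The interval is "min(91, first dose date of OLE), 210".
- **Week 52, PK and PCSK9.** The interval is "min(91, first dose date of OLE), 378". For chemistry and hematology, and for hsCRP, HbA1c, urinalysis and antibodies, it is "> min(91, first dose date of OLE" with no upper limit.
- **Blinded period for adverse events (SAP 6.3).** It runs "through min(last dose date + 30 days, EOS date, the day before OLE day 1", with no Day 91 term.
- **Blinded oral product (Protocol 3.1).** "Administration of PO IP (ezetimibe or placebo) will end with the week 12 visit for all subjects".
- **Missing Week 12 LDL-C.** It is not imputed in the repeated measures model (SAP 10.5.1.1). For the Week 12 response endpoint: "If the value is missing, the subject is considered without the achievement" (SAP 6.3). The completer analysis set requires observed co-primary values (SAP 7.2).
- **Timing.** SAP 10.1 describes the primary analysis as completed, with a data cut-off of 02 November 2017. It says the OLE summaries will be updated at final lock and the blinded-period analyses will not be repeated.

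**The concern.** Taking a minimum serves a clear purpose when the OLE dose comes first: it keeps samples taken after open-label evolocumab out of Week 12. When Day 91 comes first, the rule also turns pre-OLE samples into open-label ones. Two things follow.

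First, an LDL-C drawn before any open-label evolocumab, possibly from a subject who has taken only ezetimibe, can stand in an OLE summary as a Week 24 value. The same holds for safety laboratory or PCSK9 values at Week 52. The exposure is greatest for the Week 52 group, because the Schedule of Assessments has no draw for those analytes between Week 12 and Week 52. At the November 2017 cut, an affected subject who had not reached Week 52 would have the pre-OLE sample as the only Week 52 record. At final lock the same applies to anyone who left the extension before that visit.

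Second, the subject's Week 12 LDL-C is treated as missing in the co-primary endpoints and as a failure in a Tier 1 endpoint, although a sample exists.

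**Working it through.** **1. Apply the windows literally.** Scheduled day = 7 × week + 1, so Week 12 is Day 85 and Week 24 is Day 169. Take the sample and the first OLE dose on the same day, with the draw first.

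| Sample day | Earlier of 91 and OLE dose | Lipids | PK/PCSK9, chemistry |
|---|---|---|---|
| 85 | 85 | Week 12 | Week 12 |
| 88 | 88 | Week 12 | Week 12 |
| 91 | 91 | Week 12 | Week 12 |
| 92 | 91 | Week 24 | Week 52 |
| 99 | 91 | Week 24 | Week 52 |

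The labels are the same if no OLE dose is ever given. A Day 92 lipid sample is 92 − 85 = 7 days from Week 12 and 169 − 92 = 77 days from the week it is assigned to.

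**2. Compare with the blinded period.** Suppose the sample is on Day 92 and the first OLE dose on Day 93. With oral product taken up to the visit, the 30-day term does not bind, so an adverse event on Day 92 is a blinded-period event. The lipid sample of the same day is a Week 24 record.

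**3. When does the mislabelled value reach a table?** Appendix B keeps the record closest to the scheduled day. For Week 24 lipids, a later record up to Day 210 is at most 210 − 169 = 41 days late, so any real Week 24 sample displaces the Day 92 one. The late sample is reported only if no later record falls in the window. OLE summaries use the open-label extension analysis set, so only subjects with an OLE dose can be misreported there.

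**4. How late must the visit be?** Protocol 7.2.3.7 allows 3 days either side of Week 12, that is, up to Day 88. Day 92 is 4 days beyond that.

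**5. Is the subject still on blinded drug?** On-schedule last blinded SC doses are Day 71 (Q2W, Week 10) and Day 57 (QM, Week 8). SAP 6.3 counts SC exposure for 14 and 28 days: 71 + 14 = 85 and 57 + 28 = 85. At Day 92 the last dose is 92 − 71 = 21 or 92 − 57 = 35 days back. Daily oral product does continue to the visit.

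**6. Effect on power.** Inputs from SAP 3.2: 40 and 20 randomized, 5% never dosed (38 and 19 analysed), difference 20, SD 20, two-sided 0.05. The noncentral t has df = n1 + n2 − 2 and noncentrality 20 / (20 × √(1/n1 + 1/n2)). For 38 and 19, noncentrality is 3.56 and power is 0.938, which reproduces the stated 93%. The number of lost Week 12 values is an assumption:

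| Lost (evolocumab + ezetimibe) | n1, n2 | Power at Week 12 |
|---|---|---|
| 1 + 0 | 37, 19 | 0.936 |
| 0 + 1 | 38, 18 | 0.930 |
| 3 + 0 | 35, 19 | 0.931 |
| 2 + 1 | 36, 18 | 0.925 |
| 0 + 3 | 38, 16 | 0.909 |

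At the 37.6% effect cited from the global phase 3 study, power exceeds 0.999 in every row.

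**7. Effect on Week 12 response.** Each responder scored as a failure lowers the rate by 1/38 = 2.6 points (evolocumab) or 1/19 = 5.3 points (ezetimibe). Three evolocumab responders would be 3/38 = 7.9 points. The ezetimibe case is unlikely: screening LDL-C is at least 100 mg/dL, so reaching 70 needs a fall of about 30% or more, against the 18.1% mean reduction in Protocol 2.3.

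**The case against.** The strongest reply is that Day 91 is a sensible limit. Week 10 spans Days 64 to 77 and Week 12 spans Days 78 to 91, each 14 days. That already gives three days beyond the protocol visit window, and by Day 92 evolocumab subjects dosed on schedule are past their SC interval. The blinded period for adverse events and a visit window serve different purposes, so their ends need not coincide. Earlier visits stay in the model, and the response on the mean of weeks 10 and 12 uses whichever value is available. Losing evolocumab responders works against superiority, and the OLE tables carry no inference.

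Most of this stands. It justifies a finite upper limit for Week 12. It does not justify opening an open-label window before open-label treatment begins. The SAP gives no reason for that and no exception for pre-dose samples.

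A reader might go further in three ways that the documents do not support.

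- **Week 12 should simply run to the first OLE dose.** Protocol 6.2.1.2 has a subject who misses a visit dosed at the next scheduled one, which after Week 12 is the Week 24 clinic visit. A first OLE dose on Day 169 would then let a sample 169 − 71 = 98 days after the last scheduled Q2W dose become the co-primary value.
- **The lost sample is a fully on-treatment value.** That is clear for oral product but usually not for SC evolocumab.
- **The protocol allows a Day 92 visit.** The glossary says "QM is defined as every 4 weeks with a window of" 7 days either way, and 85 + 7 = 92. But that describes the dosing interval, while the Week 12 visit text says 3 days. The two statements need to be reconciled by the sponsor.

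**Conclusion.** The labelling defect is certain on the text. For subjects who enter the extension, a sample taken before any open-label dose can be reported as Week 24 or Week 52 open-label data, and the same subject has no Week 12 value. This is out of line with the SAP's own end of the blinded period.

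Its size is small. It requires a Week 12 visit on Day 92 or later, and the documents do not say how many there were; one to three is an assumption. On that assumption power stays about 0.93, with 0.909 as the least favourable split, and the Week 12 response rate moves by 2.6 points per evolocumab responder lost. A reader might infer that the superiority conclusion is at risk; the figures above do not support that. A reader might also infer that LDL-C could be reported as Week 52. It cannot by this route, because pre-OLE lipid samples after Day 91 go to Week 24 up to Day 210.

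**What to change.** 1. In Appendix B, for subjects with an OLE dose, set the lower limit of the Week 24 and Week 52 windows to the first OLE dose date, and apply this in the final OLE update. Pre-OLE samples after Day 91 then fall in no open-label window. State this, because Appendix B describes its intervals as generally continuous. Subjects with no OLE dose are outside the extension analysis set, so Day 91 can stay for them.
2. Keep a finite upper limit for Week 12 in the primary analysis.
3. List every subject whose pre-OLE Week 12 sample falls after Day 91, with treatment group, days since last SC and oral dose, and first OLE dose date.
4. If the list is not empty, add a sensitivity analysis of the co-primary and Week 12 response endpoints with those samples restored to Week 12 up to a stated limit, and label it as specified after unblinding.

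The cost is a wording change, a small programming change and one listing. The completed blinded-period analyses are left as they are. The drawback of the sensitivity analysis is that late evolocumab samples, Q2W and QM alike, usually lie beyond the 14- or 28-day SC interval and will tend to dilute the treatment effect.
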